9.4.3.2. Final Analysis

The final analysis will be performed for all cohorts when the end of data collection timepoint (defined in Section 5.5) is reached for all cohorts. All efficacy and safety analyses will be updated.

9.4.4. Pharmacokinetic and Pharmacodynamic Analyses

Pharmacokinetic data will be summarized and listed for all subjects with available plasma and CSF erdafitinib concentrations. Additionally, the erdafitinib CSF-to-plasma concentration ratios will be calculated with CSF and plasma PK samples collected in pair, if the sample collections of PK plasma samples and PK CSF are within 2 hours of each other. The CSF-to-plasma concentration ratios will be summarized and listed.

In addition, for children and adolescents only, the following PK parameters will be derived after serial PK sampling at Cycle 3 Day 1: C_{max} , t_{max} , AUC_{0-24h}, CL/F.

C _{max}	maximum observed analyte concentration
t _{max}	the actual sampling time to reach the maximum observed analyte concentration
AUC _{0-24h}	AUC from time of dose to 24h ^a post-dose
CL/F	total apparent clearance

^a The predose (C_{min}) sample at Cycle 4 Day 1 or other cycles in which erdafitinib has reached steady-state can be used as surrogate for 24-hour postdose PK to derive AUC₀₋₂₄.

An interim Bayesian population PK and, if appropriate, noncompartmental analysis of plasma concentration-time data of erdafitinib and markers of pharmacological activities (serum phosphate) will be performed after 5 children or adolescents (<18 years of age) are enrolled and have completed Cycle 3 Day 1 in the study. Assessment of the accuracy of the existing population PK/PD model and model parameters to predict the pediatric population PK and PK serum phosphate relation will be performed to justify or, if needed, update the age guided dose selection and phosphate guided dose titration of children and adolescent subjects.

Subjects will be excluded from the PK analysis if their data do not allow for accurate assessment of the PK (eg, missing information of dosing and sampling times; concentration data not sufficient for PK parameter calculation). All concentrations below the lowest quantifiable concentration or missing data will be labeled as such in the concentration database. All subjects and samples excluded from the analysis will be clearly documented in the study report.

Population PK analysis of plasma concentration-time data of erdafitinib may be performed using nonlinear mixed-effect modeling. Previously developed PK models may be used and updated as considered appropriate. Relationships between plasma concentrations or metrics of systemic exposure and CYP2C9 polymorphism, markers of pharmacological activities (serum phosphate), efficacy or treatment-emergent adverse events may also be explored as data allow using population approaches. If relevant, results of the analyses will be provided in a separate report.

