2.2.1. Erdafitinib

Erdafitinib is an oral pan-FGFR tyrosine kinase inhibitor shown to have in vivo antitumor activity in mouse xenograft models of FGFR-driven gastric, bladder, and non-small cell lung cancer (NSCLC) tumor models, and in patient-derived xenografts from squamous NSCLC, gastric, breast, and hepatocellular tumors.

In humans, erdafitinib exhibited a dose-related increase in the maximum plasma drug concentration (C_{max}) and area under the curve (AUC) and time-independent pharmacokinetics (PK) within the dose range of 0.5 mg to 12 mg, both after single and multiple daily dosing. Median time to maximum concentration observed ranged from 2 to 4 hours (erdafitinib as capsule). Relative bioavailability was comparable under fed and fasted conditions. Erdafitinib is highly bound to plasma proteins such as α 1-acid glycoprotein (α 1-AGP). Free fractions of erdafitinib in human plasma were small (average~0.36%). Erdafitinib is a P-glycoprotein (P-gp) substrate.

An in vitro metabolism study in human liver microsomes and hepatocytes showed major involvement of cytochrome P 450 (CYP) enzymes CYP2C9 and CYP3A4. Long terminal phase half-life of erdafitinib (>50 hours) in plasma was observed resulting in approximately 3-fold accumulation of C_{max} and AUC following multiple daily dosing.

In a Phase 1 study (Study 42756493EDI1001, n=187), the antitumor effect of erdafitinib was observed in subjects with urothelial cancer with selected FGFR aberrations, as well as other solid tumors. For all subjects with relapsed/refractory urothelial cancer, the overall response rate (ORR) across dose levels was 40.0% (12/30 subjects). At the 9 mg dose level, ORR was 70.0% (7/10 subjects) for response-evaluable subjects with urothelial cancer who harbored selected FGFR aberrations. The most frequently reported adverse events (AEs) were hyperphosphatemia (65%), dry mouth (46%), asthenia (45%), stomatitis (39%), constipation (37%), and decreased appetite (34%).

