Identify FGFR mutations and tumor histologies sensitive to erdafitinib from the Exploratory Cohort	FGFR mutations and tumor histologies with clinical response to erdafitinib which are not represented in the Broad Panel Cohort.
To explore PK exposure-response relationships	Quantitative relationship between PK exposure parameters, pharmacodynamic (PD) parameters (serum phosphate), and safety/efficacy parameters
To assess tumor-specific biomarkers (DNA, RNA, protein) in archival tumor samples, and possibly blood that potentially predict tumor response or resistance to erdafitinib	Analysis of co-occurring genomic alterations from archival tumor samples
To evaluate the relationship between CYP2C9 polymorphism and PK of erdafitinib	Effect of CYP2C9 polymorphism on the PK of erdafitinib
To assess the distribution of erdafitinib in the cerebrospinal fluid (CSF) (when available)	Erdafitinib concentration in CSF, ie, the CSF-to-plasma concentration ratios
To collect Medical Resource Utilization data that may be used in future economic models	Evaluation of all the health states generated by the EQ-5D-5L utility and visual analog scale (VAS).

Refer to Section 8, Study Assessments and Procedures for evaluations related to endpoints.

Hypothesis

The primary hypothesis of this study is that treatment with erdafitinib orally once daily will improve ORR with a target rate of 35% over a null rate of 15% in subjects with advanced solid tumors that harbor target FGFR alterations in the Broad Panel Cohort, the Core Panel Cohort, or both cohorts. Comparable response from erdafitinib treatment is expected in the pediatric and adult study populations, ie, a 35% of ORR with a null hypothesis of 15% for ORR.

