8.5. Pharmacokinetics

Venous blood samples (2 mL per visit) will be collected for the determination of plasma concentrations of erdafitinib at the time points specified on the Schedule of Activities (Section 1.3 for Adults and Section 1.4 for Children and Adolescents). On PK sampling days Cycle 1 Day 14, and Cycle 2 Day 14 (children and adolescents only), for morning clinic visits, morning dosing should be withheld until after the PK sample has been obtained in the clinic. For afternoon clinic visits, subjects should take their dose as usual and a postdose sample should be collected during the visit. On Cycle 2 Day 1, Cycle 3 Day 1 (children and adolescents only), and Cycle 4 Day 1 (children and adolescents only), the dose should be taken in the clinic after the predose PK sample. On Cycle 2 Day 1, a 2- to 4-hour blood sample will be collected for adults, children, and adolescents. An approximate 1-4-mL venous blood sample will be taken together with the postdose PK samples on Cycle 2 Day 1, 2- to 4-hour postdose (for adults), and Cycle 3 Day 1, 2-hour postdose (for children and adolescents) for the determination of plasma protein binding data of erdafitinib (ie, alpha-1-acid glycoproteins, total protein, and fraction unbound) (Section 1.3 for adults and Section 1.4 for children and adolescents). On Cycle 3 Day 1, serial PK samples will be collected at predose, and at 1h, 2h, 4h, 6h, 12h postdose in children and adolescents. The 12h postdose sample can alternatively be collected at 24h postdose (see Section 1.4). The time of dosing, and the time of the PK sample and protein binding sample must be recorded accurately. If indicated by the emerging safety findings or if the scheduled PK samples are not collected due to treatment interruption, blood samples may be collected at a later site visit (on Cycle 2 Day 14 [adults only], Cycle 3 Day 1 [adults only], or Cycle 3 Day 14). In the event of a treatment interruption of 2 consecutive weeks or more, PK samples do not need to be collected. The Laboratory Manual provides further information regarding handling and shipment of blood/plasma samples.

Germline DNA will be collected for subjects on erdafitinib (see Schedule of Activities in Section 1.3 for Adults and Section 1.4 for Children and Adolescents) from a blood sample (2 mL) on Cycle 1 Day 14 (or later timepoint) for the purpose of CYP2C9 genotyping to allow exploration of the effect of CYP2C9 polymorphism on the PK of erdafitinib.

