8.5.1. Analytical Procedures

Blood samples will be processed to obtain plasma for measurement of erdafitinib concentration by a validated analytical method under the direction of the sponsor. Plasma protein binding, if needed, will be determined by equilibrium dialysis. After dialysis, the buffer and plasma samples will be analyzed for erdafitinib content using a qualified liquid chromatography/mass spectrometry method by the sponsor's Bioanalytical Laboratory. The α 1-AGP and other proteins will also be measured in the plasma protein binding samples. CSF samples will be analyzed for erdafitinib concentrations using a qualified liquid chromatography/mass spectrometry method by the sponsor's Bioanalytical Laboratory.

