7. PHARMACOKINETICS (PK)

Details of population PK analysis, analysis to evaluate relationships between plasma concentration or metrics of systemic exposure and CYP2C9 polymorphism, markers of pharmacological activities (serum phosphate), efficacy or treatment-emergent adverse events may be explored as data allow using population approaches. If relevant, these analyses will be presented in a separate plan and results will be presented in a separate report. All subjects and samples excluded from the analysis will be clearly documented in the separate study report.

Plasma and CSF pharmacokinetic data will be listed for all subjects with available plasma erdafitinib concentrations. Concentration values below the lower limit of quantitation (LLOQ) will be displayed in listings as zero with a flag and handled as zero. Plasma protein binding data such as alpha-1-acid glycoprotein and fraction unbound (unitless) of erdafitinib based on assessment on C2D1 2-4 hour postdose will be listed for all subjects.

For Pediatric Cohort, an interim Bayesian population PK analysis and, if appropriate, NCA analysis of plasma concentration-time data for erdafitinib and markers of pharmacological activities (e.g., serum phosphate) will be performed after 5 children or adolescents (<18 years of age) are enrolled and have completed Cycle 3 Day 1 visit in the study (see protocol Section 9.4.4). In addition, further interim analyses may be conducted after enrollment of additional subjects. Descriptive statistics, including arithmetic and geometric mean, median, standard deviation, coefficient of variation (CV), geometric CV, minimum and maximum, will be tabulated for erdafitinib PK concentrations and protein binding data by time point and age groups (children [6 to <12], adolescents [12 to <15 years of age, 15 to <18 years of age]). PK and protein binding summary table will be performed based on PK analysis set.

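### The exploratory CSF-to-plasma ratio mixes plasma protein binding with CSF penetration, and CSF values below LLOQ are handled as zero

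*Protocol*

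**What the plan says.** Protocol 3 states the exploratory objective as "To assess the distribution of erdafitinib in the cerebrospinal fluid (CSF) (when available"), and its endpoint as "Erdafitinib concentration in CSF, ie, the CSF-to-plasma concentration ratios". Protocol 9.4.4 plans summaries and listings of the plasma and CSF concentrations themselves. It then adds that "the erdafitinib CSF-to-plasma concentration ratios will be calculated with CSF and plasma PK samples collected in pair", provided the two draws fall within 2 hours of each other. No unbound correction is given, and no reference value for reading the ratio.

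Protocol 8.5.1 describes the assays. For plasma: "Blood samples will be processed to obtain plasma for measurement of erdafitinib concentration by a validated analytical method". For CSF: "CSF samples will be analyzed for erdafitinib concentrations using a qualified liquid chromatography/mass spectrometry method". Unbound drug is obtained separately, by equilibrium dialysis of plasma, and only where it is needed. Neither document applies the word total to the ratio, but that is what these assays imply.

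On binding, Protocol 2.2.1 says "Free fractions of erdafitinib in human plasma were small (average~0.36" (a percentage). Protocol 8.5 draws a further blood sample "for the determination of plasma protein binding data of erdafitinib (ie, alpha-1-acid glycoproteins, total protein, and fraction unbound"), on Cycle 2 Day 1 in adults and Cycle 3 Day 1 in children and adolescents. SAP 7 lists the binding results but cites only the Cycle 2 Day 1 sample. It does not link fraction unbound to CSF and does not mention the ratio.

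For low concentrations SAP 7 says "Concentration values below the lower limit of quantitation (LLOQ) will be displayed in listings as zero with a flag and handled as zero". Protocol 9.4.4 asks only that such values be marked in the database and names no substitute value.

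**The concern.** CSF is sampled in subjects with CNS tumors. High-grade and low-grade glioma are named histologies in Protocol Table 16, and Protocol 2.2.1 describes the drug as a P-gp substrate, so how much drug reaches the CSF is a reasonable question. The chosen scale makes the answer hard to read. When almost all plasma drug is bound and CSF holds little binding protein (an assumption; the documents do not say), complete penetration sits far below 1 on a total-over-total scale. With no reference value in the plan, a small ratio could be taken for poor penetration.

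Two subjects with equal penetration but different plasma binding would also show different ratios, so the spread between subjects cannot be attributed to penetration. The zero rule adds a further problem: it records a ratio of 0 where the data support only a statement that the ratio lies below some bound.

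**Working it through.** The plan gives no expected ratio, precision or sample size for this endpoint, so there is no planned figure to reproduce.

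**Inputs.** The free fraction in plasma is fu = 0.0036 (Protocol 2.2.1), so the bound share is 1 - 0.0036 = 99.64%. The free fraction in CSF, the LLOQ and the plasma concentrations are not in the documents. Binding in CSF is therefore assumed and shown as a range.

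**Formula.** Let K be unbound CSF over unbound plasma, with K = 1 for complete penetration. Then

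total CSF / total plasma = K x fu / fu(CSF).

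**Step 1: no binding in CSF, fu(CSF) = 1.**

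| Penetration K | Ratio |
|---|---|
| 1 | 0.0036 |
| 0.5 | 0.0018 |
| 0.1 | 0.00036 |
| 0.01 | 0.00004 |

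The ratio is proportional to K.

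**Step 2: some binding in CSF, K = 1.** With fu(CSF) = 0.75 the ratio is 0.0036 / 0.75 = 0.0048. With 0.5 it is 0.0072. If CSF binding protein is a share r of plasma protein and binding is linear, the ratio is fu + r(1 - fu). For r = 0.1% this is 0.0036 + 0.0010 = 0.0046, and for r = 1% it is 0.0036 + 0.0100 = 0.0136. Over these assumptions complete penetration reads as about 0.004 to 0.014.

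**Step 3: plasma binding varies between subjects.** Take an observed ratio of 0.0036, no CSF binding, and an assumed fu range of 0.002 to 0.007. Then K = 0.0036 / fu:

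| fu | K |
|---|---|
| 0.002 | 1.8 |
| 0.0036 | 1.0 |
| 0.005 | 0.72 |
| 0.007 | 0.51 |

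The same ratio corresponds to a 3.5-fold range of penetration (0.007 / 0.002).

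**Step 4: the zero rule.** With no CSF binding, complete penetration is quantifiable only if total plasma is at least 1 / 0.0036 = 278 times the CSF LLOQ. The documents do not let anyone check this. The direction of the effect is clear all the same. If every subject had a true ratio of 0.0036 and a share q of CSF values were set to zero, the reported mean would be (1 - q) x 0.0036: 0.0027, 0.0018 or 0.0009 for assumed q of 25%, 50% or 75%. These shares are illustrations, not predictions. SAP 7 also plans geometric means of pediatric PK concentrations; if CSF values are included, a single zero leaves the geometric mean undefined on the log scale.

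**Step 5: what the correction does.** CSF / (plasma x fu) equals K / fu(CSF). With negligible CSF binding, complete penetration reads as 1.0. With the heaviest CSF binding assumed in Step 2 it reads as 0.0136 / 0.0036 = 3.8, so the CSF assumption must be stated with the result. For a value below LLOQ, unbound CSF cannot exceed total CSF, so K is below LLOQ / (plasma x fu) whatever the CSF binding, given the right fu.

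**The case against.** The strongest reply is that the ratio does carry the information. It separates complete from 10% penetration tenfold (0.0036 against 0.00036), any quantifiable CSF level shows that drug has reached the CSF, and the 0.36% needed to read the ratio is printed in the protocol. Protocol 9.4.4 also reports the concentrations themselves, and SAP 7 lists fraction unbound and flags values below LLOQ. All of this stands. A reader might infer from the small numbers that the planned measure cannot show CSF distribution, or that the objective cannot be answered. The documents do not support that reading.

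A reader might also infer that most CSF values will fall below LLOQ. That is not supported either: no LLOQ or plasma level is given, and CSF has its own assay method. Because SAP 7 never mentions the ratio, carrying the zero into it is itself an inference from the rule as worded.

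Two further points bear on the remedy. Dividing by a fixed 0.36% only rescales the ratio and does not remove between-subject binding. And the binding sample is tied to a set cycle day, not to the CSF draw, so an individual fu may not match the fu on the day of the draw.

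What the reply does not meet is that neither document pre-specifies the step from ratio to penetration, and that a flag in a listing does not undo a zero used in a summary.

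**Conclusion.** The point holds as a low-severity improvement. The ratio scales with penetration, but it cannot be read as the degree of CSF penetration until it is corrected for unbound drug. At complete penetration it would be about 0.0036 with negligible CSF binding, and about 0.004 to 0.014 over the assumed CSF binding. Differences in plasma binding are mixed into differences between subjects. Handling values below LLOQ as zero turns a non-quantifiable CSF result into a ratio of 0 and biases summaries downward; the direction is clear and the size cannot be given.

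This rests on the total-over-total reading of the assays, on the average free fraction in Protocol 2.2.1, and on assumed CSF binding. The endpoint is exploratory, draws on routine CSF procedures when feasible, and has no hypothesis test.

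**What to change.** In Protocol 9.4.4 and SAP 7:

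- Pre-specify CSF / (paired plasma x the subject's fraction unbound) alongside the raw ratio, with the assumption of negligible CSF binding stated, and add both ratios to SAP 7.
- Run the fraction-unbound assay for every subject with a CSF sample, using the binding sample already drawn: Cycle 2 Day 1 in adults, Cycle 3 Day 1 in children and adolescents. Amend SAP 7, which now cites only Cycle 2 Day 1. If a subject's value is missing, use 0.36% and flag the result.
- Report CSF values below LLOQ as a count and an upper bound, LLOQ / (paired plasma x fraction unbound), not as zero.

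The cost is a wording change, a derived column and a few extra assays on samples already collected. No visit or blood draw is added. The correction remains approximate, because the binding sample may come from a different day than the CSF draw.

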9.4.5. Biomarker Analyses

Changes in molecular markers (FGFR or other genes), disease relevant biomarkers, and phosphate levels over time will be summarized by treatment group. Associations between baseline levels and changes from baseline in select markers and clinical response will be explored.

Results of exploratory biomarker analyses may be presented in a separate report. Planned biomarker analyses may be deferred if emerging study data show no likelihood of providing useful scientific information.

9.4.6. Medical Resource Utilization and Patient-reported Outcomes Analyses

Medical resource utilization and PRO measures will be summarized descriptively (ie, mean, standard deviation including change from baseline) at each assessment time point. Additional analyses may be conducted; details and results of any additional analyses will be presented in a separate report.

9.4.7. Safety Analyses

Adverse Events

The verbatim terms used in the CRF by investigators to identify adverse events will be coded using the Medical Dictionary for Regulatory Activities (MedDRA). Treatment-emergent adverse events are adverse events with onset during the Treatment Phase or that are a consequence of a pre-existing condition that has worsened since baseline. All reported treatment-emergent adverse events will be included in the analysis. For each adverse event, the percentage of subjects who experience at least 1 occurrence of the given event will be summarized by intervention group. In addition, comparisons between intervention groups will be provided if appropriate.

Summaries, listings, datasets, or subject narratives may be provided, as appropriate, for those subjects who die, who discontinue intervention due to an adverse event, or who experience a severe or a serious adverse event.

Clinical Laboratory Tests

Laboratory data will be summarized by type of laboratory test. Reference ranges and markedly abnormal results (specified in the Statistical Analysis Plan) will be used in the summary of laboratory data. Descriptive statistics will be calculated for each laboratory analyte at baseline and at each scheduled time point. Changes from baseline results will be presented in pre- versus post-intervention cross-tabulations (with classes for below, within, and above normal ranges). Frequency tabulations of the abnormalities will be made. A listing of subjects with any laboratory results outside the reference ranges will be provided. A listing of subjects with any markedly abnormal laboratory results will also be provided. Parameters with predefined NCI-CTCAE toxicity grades will be summarized. Change from baseline to the worst adverse event grade experienced by the subject during the study will be provided as shift tables.

Electrocardiogram

Electrocardiogram data will be summarized by ECG parameter. Descriptive statistics will be calculated at baseline and for observed values and changes from baseline at each scheduled time point. Frequency tabulations of the abnormalities will be made.

The ECG variables that will be analyzed are heart rate, PR interval, QRS interval, QT interval, and QT corrected according to Fridericia's formula (QTcF). The Bazett formula may be used for children and adolescent subjects. Descriptive statistics of QTc intervals and changes from baseline will be summarized at each scheduled time point. The percentage of subjects with QTc interval >450 milliseconds, >480 milliseconds, or >500 milliseconds will be summarized, as will the percentage of subjects with QTc interval increases from baseline >30 milliseconds or >60 milliseconds. All clinically relevant abnormalities in ECG waveform that are changes from the baseline readings will be reported (eg, changes in T-wave morphology or the occurrence of U-waves).

ECOG

ECOG grade will be summarized at each scheduled time point. Descriptive statistics will be calculated at baseline and for observed values and changes from baseline at each scheduled time point.

Bone-related Assessments

Descriptive statistics will be calculated at baseline and for observed values and changes from baseline at each scheduled time point.

[figure not shown]
